## 10. Power Calculations

**a) Aim 1:** Effect sizes were estimated for the primary endpoints of  $FMD_{BA}$  and aPWV based on published data of a similar population. We hypothesize that participants randomized to the bicarbonate group will have an improvement (i.e., increase) in  $FMD_{BA}$  at 12 months, while those in placebo will have a decrease in  $FMD_{BA}$ . We will compare change (from baseline to 12 months) in  $FMD_{BA}$  between the two groups. A previous study of paricalcitol vs. placebo in CKD stage 3-4 showed a between group difference of 1.8% in changed  $FMD_{BA}$  with 95% CI 0.3-3.1% after 12 weeks. Our preliminary data showed a between group difference (bicarbonate vs. control) of 1.6% in changed  $FMD_{BA}$  with 95% CI 0.2-2.9% after 6 weeks. Assuming a standard deviation of change of 0.8%, 54 patients in the placebo group and 54 patients in the bicarbonate group achieves 99% power to detect a 1.5% difference among the means (which is a clinically meaningful difference) using the two sample t-test with a two-sided 0.025 significance level (i.e. 5% significance level after Bonferroni correction for 2 outcomes) for intent-to-treat (ITT) analysis. It would also achieve 99% power to detect the same effect size in per-protocol analysis (n=45 per group allowing for 15% attrition). We hypothesize that participants randomized to the bicarbonate group will have no change or a decrease in arterial stiffness measured by aPWV at 12 months, while those in placebo will have an increase in stiffness. We will compare change (from baseline to 12 months) in aPWV between the two groups. In previous studies of CKD patients with comparable kidney function, the mean (SD) increase in aPWV was  $1.1 \pm 1$  m/s over a 12 month period. Assuming a common standard deviation within a group of 1.5 m/s, 54 patients in each group will provide 88% power to detect a 1.0 m/s difference among the means (which is a clinically significant difference) using the two sample t-test with a two-sided 0.025 significance level (i.e. 5% significance level after Bonferroni correction for 2 outcomes) for ITT analysis. It would also achieve 80% power to detect the same effect size in per-protocol analysis (n=45 per group allowing for 15% attrition).

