## 11. Statistical Analysis

- **General consideration:** The primary analysis will be conducted on ITT basis. Analysis of covariance (ANCOVA) with complete data will be the primary analysis for efficacy. Multiple imputation will apply because of missing data and sensitivity analysis will be conducted in various ways, including linear mixed effects model and pattern-mixture model approach. Compliance of intervention will be summarized using the number of pills taken as the proportion of planned number of pills. The association of compliance with each of the outcomes ( $FMD_{BA}$  aPWV and LVMI) will be explored using multiple linear regression. Participants who receive rescue therapy will be analyzed in the ITT analysis but excluded from the per-protocol analysis. We will also analyze the data with and without adjustment for change in eGFR, exploring its potential effect. All analyses will be performed using SAS version 9.4 (SAS Institute, Cary, NC, USA).
- **Descriptive statistics:** Descriptive statistics of baseline characteristics and outcomes variables will be provided for all enrolled participants; mean and standard deviation for continuous variable and proportion for categorical variable. Summaries will be provided for the full cohort and for subgroups defined by age, gender, and baseline kidney function. Highly-skewed variables may be transformed prior to statistical analyses to better approximate normality. Change over time in outcome variables will be presented by using appropriate charts and tables.
- **Analysis Plan for Aim 1:** The goal of this aim is to compare changes from baseline to 12 months in  $FMD_{BA}$  and aPWV between the two groups and ANCOVA will be used to test the difference. In all analyses, a  $p \leq 0.025$  will be considered significant. Furthermore, we will investigate how  $FMD_{BA}$  and aPWV change over time in one year by using longitudinal data analysis with mixed effect models. We will perform analysis of response profile in which we will assess the mean level of  $FMD_{BA}$  and aPWV at all time points in each group and examine for differences between groups at each time point. In addition, will assess for an effect of the intervention vs. placebo prior to the end of study. We will also fit parametric curves if exploratory analyses find a curve pattern of change over time in  $FMD_{BA}$  and aPWV.

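### The supplementary response-profile analysis of FMD and aPWV is written as arm differences in mean level at every visit, baseline included, with no baseline adjustment stated; a baseline-adjusted contrast would be more precise at no cost

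*Combined protocol and SAP*

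**What the plan says.** In section 11 (Statistical Analysis), the general considerations make ANCOVA the main efficacy method: "Analysis of covariance (ANCOVA) with complete data will be the primary analysis for efficacy". The Aim 1 plan applies it to the change from baseline to 12 months in FMD and aPWV "between the two groups and ANCOVA will be used to test the difference", with p ≤ 0.025 counting as significant in all Aim 1 analyses.

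The same paragraph then adds a supplementary analysis of how the two outcomes "change over time in one year by using longitudinal data analysis with mixed effect models". Its working part is a response profile: the mean level of each outcome is assessed "at all time points in each group and examine for differences between groups at each time point". A further sentence promises an assessment of effect before the end of study, without naming the contrast. Parametric curves are to be fitted if a curved pattern appears.

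For this longitudinal analysis the plan states no baseline covariate, no constraint of a common baseline mean and no change-from-baseline contrast. By section 8 (Data Collection), FMD is measured at baseline, month 1 (optional), month 6 and month 12, and aPWV at baseline, month 6 and month 12. Baseline is therefore one of the time points.

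**The concern.** Baseline is measured before randomisation, so any difference between the arms there is chance. A contrast of mean levels at a later visit carries part of that chance difference with it, and it forgoes the precision available from each participant's own baseline value. For a stable quantity such as aPWV that precision may be large.

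Moving to a mixed model does not cure this by itself. If baseline is one of the responses and each arm has its own free baseline mean, then with complete data the estimated arm difference at month 12 is simply the difference in month-12 means.

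The response profile is the one analysis with a stated contrast that covers the visits before month 12. It could disagree with the month-12 ANCOVA through baseline imbalance alone. Read literally, it also compares the arms at baseline, which answers no question in a randomised trial.

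**Working it through.** **Inputs.** From section 10 (Power Calculations), Aim 1, for aPWV: "54 patients in each group will provide 88% power to detect a 1.0 m/s difference among the means", "Assuming a common standard deviation within a group of 1.5 m/s", and a test "using the two sample t-test with a two-sided 0.025 significance level". For FMD: SD of change 0.8%, difference 1.5%, 54 per arm. The correlation rho between baseline and follow-up is not in the documents, so it is an assumed range. Equal variances at the two visits are assumed.

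**The plan's own figure.** The standard error is 1.5 × sqrt(2/54) = 0.289, the noncentrality is 1.0/0.289 = 3.46, and the two-sided 0.025 critical value on 106 df is 2.274. Noncentral-t power is 88.1%, against 88% stated. With 45 per arm it is 80.9%, against 80% stated. Both reproduce.

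**Formulas.** Let s be the SD of the level at a visit.
- Unadjusted difference in level: variance (2/n)s².
- Baseline-adjusted difference: variance (2/n)s²(1 − rho²).
- Ratio: 1/(1 − rho²).
- If the stated SD is that of change, s = 1.5/sqrt(2(1 − rho)).

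**aPWV power, 1.5 m/s read as the SD of change** (54 per arm, 1.0 m/s)

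| rho | SD of level | Adjusted SD | Unadjusted power | Adjusted power | Variance ratio |
|---|---|---|---|---|---|
| 0.3 | 1.27 | 1.21 | 96% | 98% | 1.10 |
| 0.5 | 1.50 | 1.30 | 88% | 96% | 1.33 |
| 0.7 | 1.94 | 1.38 | 66% | 93% | 1.96 |
| 0.8 | 2.37 | 1.42 | 47% | 91% | 2.78 |

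**aPWV power, 1.5 m/s read as the SD of the level.** Unadjusted power is 88% at every rho. The adjusted SD is 1.5 × sqrt(1 − rho²) = 1.43, 1.30 and 1.07 at rho 0.3, 0.5 and 0.7, giving 91%, 96% and above 99%.

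**Check in the mixed model.** Generalised least squares was run for three visits with compound symmetry, complete data and 54 per arm. Month-12 contrast variances, in units of s², were:

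| rho | Level difference, free baseline means | Arm-by-visit change contrast | Common baseline mean |
|---|---|---|---|
| 0.3 | 0.0370 | 0.0519 | 0.0337 |
| 0.5 | 0.0370 | 0.0370 | 0.0278 |
| 0.7 | 0.0370 | 0.0222 | 0.0189 |
| 0.8 | 0.0370 | 0.0148 | 0.0133 |

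The first column equals 2/54 throughout, so baseline adds nothing to it. The last column equals (2/54)(1 − rho²), the ANCOVA value.

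**Size of the imbalance carried** (SD-of-change reading). A one-standard-error baseline difference is s × sqrt(2/54) = 0.29, 0.37 and 0.46 m/s at rho 0.5, 0.7 and 0.8. Multiplied by rho, it shifts the expected visit difference by 0.14, 0.26 and 0.37 m/s, against a target of 1.0 m/s.

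**FMD.** At rho 0.9, s = 0.8/sqrt(0.2) = 1.79%, and unadjusted power for 1.5% is still 98%. At lower rho it is higher.

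**The case against.** A reader might infer that the plan chose raw means over adjusted ones. The documents do not support that. They are silent on baseline handling, the mixed models are introduced to study change over time, and a model with arm, visit and their interaction can also give an arm difference in change, which is neither specified nor excluded. This stands: the fault is a contrast written without adjustment, not a rejection of adjustment. A change contrast would still be less precise than an adjusted one, as the third column of the variance table shows.

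A reader might also infer that the trial's main result is at risk, or biased. Neither follows. The primary test is the month-12 ANCOVA, the power section covers only month-12 change, and randomisation keeps the level contrast unbiased on average.

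The size is open to fair challenge. Rho is assumed, and at 0.3 little is lost. Only the FMD figure is expressly called an SD of change. The 66% and 47% for aPWV depend on reading 1.5 m/s the same way, which inflates the SD of the level to 1.94 and 2.37 m/s. All the power figures use the month-12 effect with 54 complete per arm, so they illustrate the loss and do not measure power at month 6. aPWV is not measured at month 1 at all.

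With dropout, a mixed model with free baseline means does recover something from baseline. At rho 0.7, with 9 of 54 per arm having baseline only, the month-12 variance is 0.0408 against 0.0444 for the 45 observed cases alone. The common-baseline model gives 0.0227, so most of the gain is still left unused.

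Finally, the sentence on effects before the end of study names no contrast, so it cannot be assumed to be the unadjusted one. Equally, it supplies no adjusted one.

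**Conclusion.** The point holds for a supplementary analysis. As written, the visit-wise contrast is a difference in mean levels with no baseline term; it carries chance baseline imbalance and has 1.10 to 2.78 times the variance of a baseline-adjusted contrast for rho from 0.3 to 0.8. For aPWV the power cost is 2 percentage points or less at rho 0.3 and 27 points at 0.7 on the SD-of-change reading. On the SD-of-level reading it is about 3 points at 0.3 and about 11 at 0.7. Adjustment is better on both readings. For FMD, the plan's own SD of change leaves power at about 98% or more up to rho 0.9.

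These sizes rest on an assumed rho, equal variances, complete data and the month-12 effect. The powered comparison and the primary conclusion are untouched. This is a free improvement to the analysis of time course, not a defect in the trial's main test.

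**What to change.** In the Aim 1 plan of section 11, specify that the longitudinal analysis is a mixed model with one baseline mean common to both arms, or equivalently post-baseline values with baseline value by visit as covariate. Report the arm difference with its confidence interval at post-baseline visits only: months 6 and 12 for aPWV; months 6 and 12 for FMD, plus month 1 in those who had the optional measurement. Drop the comparison of the arms at baseline. In the same edit, name the baseline value as the ANCOVA covariate, because section 11 lists no covariates for it.

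The cost is a few lines of SAP text and SAS code. It uses data already planned for collection and changes neither the sample size nor the primary test.

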## 12. Potential Problems and Alternative Strategies

- Although subject recruitment and retention are always challenging, we should be able to complete the study in the proposed timeline given our groups excellent track record in recruiting and enrolling participants in clinical trials. The PI completed a randomized clinical trial of 128 patients with CKD stage 3B-4 and all patients were enrolled within 3 years (K23 DK087859).
- We should have few difficulties with the proposed experimental procedures and protocols as they are already established in the vascular laboratories at the University of Colorado Denver. The PI has extensive experience with the vascular function measurements outlined in this proposal and the investigative team has experience with performing cardiac MRIs in patients with CKD.
- We recognize that alternative approaches exist for examining the effects of alkali therapy on CVD in patients with CKD. For example, one alternative would be to undertake a larger study to examine hard cardiovascular endpoints rather than the investigation proposed in the current application. However, our proposed study is the most cost-effective approach to obtain confirmation of the study hypotheses and to determine the endpoints to use in a future clinical outcomes trial.
- We recognize that different dosages of sodium bicarbonate therapy can be used. However, the proposed dose in the current study has been shown to be safe and effective in treating metabolic acidosis in published reports and in our completed pilot study with CKD stage 3-4 patients.

- We acknowledge that  $T_{50}$  has not been validated as a measure of vascular calcification. However, aortic calcification is strongly associated with aPWV and reduced  $T_{50}$  is independently associated with progressive aortic stiffness in patients with CKD.
- Systolic BP is an important determinant of endothelial function, arterial stiffness and LVH and could be a theoretical confounder when interpreting the mechanisms by which alkali therapy improves EDD, aPWV and LVMI. However, we do not expect this to be an issue as all participants must have their BP controlled prior to entering the study. Patients will undergo a run-in phase to ensure their BP is controlled to <130/80 mmHg and to achieve a stable antihypertensive regimen, such that changes in antihypertensive agents throughout the course of the study are minimal. Additionally, we will adjust for BP if differences in BP control is observed between the groups. In our preliminary pilot study we did not see any differences in BP between the treatment and control conditions (see section 1c).
- We acknowledge that there may be other potential mechanisms by which acid retention results in arterial dysfunction. Acidosis induces inflammation (risk factor for arterial dysfunction) and net calcium and phosphate efflux from bone (risk factor for calcification). Hence, we will measure markers of inflammation (cytokine 12 panel (IL-2, IL-4, IL-5, IL-6, IL-8, IL-10, IL-13, Interferon gamma, IL-2 Receptor, IL-1 beta, tumor necrosis factor) and markers of bone metabolism (serum parathyroid hormone, bone specific alkaline phosphatase and beta C-terminal telopeptide).

### **Optional Cognitive and Motor Function Testing**

Participants will be given the option to participate in optional cognitive and motor function testing on the consent form. Cognition refers to the mental processes involved in gaining knowledge and comprehension such as thinking, knowing, remembering, judging and problem-solving. Measurement of cognition is essential to study health and well-being. Motor function is the ability to use and control muscles and movements. Motor performance is indicative of physical health, burden of disease and long term health outcomes. It is also related to a person's daily functioning and quality of life. No additional study visits will be needed. These function measures will be done at the baseline, 6-month and 12-month visits. They will be assessed with the NIH Toolbox tests. These tests will add approximately 38 minutes onto the study visits. There is no additional risk to the patients.

**1. Cognition.** Cognitive function will be assessed using the NIH Toolbox computerized tests to evaluate 1) attention, 2) episodic memory, 3) working memory, 4) language, 5) executive function, and 6) processing speed. Administering the NIH Toolbox cognitive battery will yield the following summary scores, in addition to individual measure scores: Cognitive Function Composite Score ('g' factor, or general cognitive ability based on performance of each subdomain), Fluid Cognition Composite Score (includes tests of attention, executive function, working memory, and processing speed) and Crystallized Cognition Composite Score (includes Picture Vocabulary and Reading Recognition measures).

#### **Cognitive and Motor Outcomes using NIH Tool Box**

	Subdomain	Assessment
Cognitive	Attention	Flanker inhibitory control & Attention Test
	Episodic memory	Picture sequence memory
	Working memory	List sorting working memory
	Language	Picture vocabulary Oral reading recognition
	Executive function	Flanker inhibitory control Dimensional change card sort
	Processing speed	Pattern comparison
Motor	Dexterity	9-Hole Pegboard Dexterity Test
	Strength	Grip Strength Test

**NIH Toolbox Cognitive Domain:** computerized tests will be administered at the Kidney Research center during the baseline, 6-month and 12-month visits.

**Attention (NIH Toolbox).** Attention will be measured by the NIH Toolbox Inhibitory Control and Attention Test. The Flanker task measures both a participant's attention and inhibitory control. The test requires the participant to focus on a given stimulus while inhibiting attention to stimuli (fish for ages 3-7 or arrows for ages 8-85) flanking it. Sometimes the middle stimulus is pointing in the same direction as the "flankers" (congruent) and sometimes in the opposite direction (incongruent). Scoring is based on a combination of accuracy and reaction time.

**Episodic Memory (NIH Toolbox).** Episodic Memory refers to cognitive processes involved in the acquisition, storage and retrieval of new information and will be measured with the NIH Toolbox Picture Sequence Memory Test. The Picture Sequence Memory Test is a measure developed for the assessment of episodic memory. It involves recalling increasingly lengthy series of illustrated objects and activities that are presented in a particular order on the computer screen. The participants are asked to recall the sequence of pictures that is demonstrated over two learning trials; sequence length varies from 6-18 pictures, depending on age. Participants are given credit for each adjacent pair of pictures (i.e., if pictures in locations 7 and 8 are placed in that order and adjacent to each other anywhere – such as slots 1 and 2 – one point is awarded) they correctly place, up to the maximum value for the sequence, which is one less than the sequence length (if there are 18 pictures in the sequence, the maximum score is 17, because that is the number of adjacent pairs of pictures that exist).

**Working Memory (NIH Toolbox).** Working Memory refers to a limited-capacity storage buffer that becomes overloaded when the amount of information exceeds capacity and is measured by the NIH Toolbox List Sorting Working Memory Test. This test requires immediate recall and sequencing of different visually and orally presented stimuli. Pictures of different foods and animals are displayed with accompanying audio recording and written text (e.g., "elephant"), and the participant is asked to say the items back in size order from smallest to largest, first within a single dimension (either animals or foods, called 1-List) and then on 2 dimensions (foods, then animals, called 2-List). The score is equal to the number of items recalled and sequenced correctly.

**Language (NIH Toolbox).** NIH Toolbox focuses on two aspects of language: vocabulary knowledge, which is fundamental to the growth of knowledge and which also has a very high association with overall intelligence, or what has been called the "g factor", and oral reading skill, which reflects level and quality of prior educational experiences, and provides a fairly robust indication of verbal intelligence that is relatively undisturbed by many medical conditions that affect the brain. Vocabulary language will be measured by the NIH Toolbox Picture Vocabulary Test while oral reading will be measured by the NIH Toolbox Oral Reading Recognition Test. The NIH Toolbox Picture Vocabulary Test measures receptive vocabulary and is administered in a computerized adaptive format. The respondent is presented with an audio recording of a word and four photographic images on the computer screen and is asked to select the picture that most closely matches the meaning of the word.

During NIH Toolbox Oral Reading Recognition Test the participant is asked to read and pronounce letters and words as accurately as possible. The test administrator scores them as right or wrong. The test is given in a computerized adaptive format.

**Executive Function (NIH Toolbox).** Executive Function is the capacity to plan, organize, and monitor the execution of behaviors that are strategically directed in a goal-oriented manner and is measured by the NIH Toolbox Dimensional Change Card Sort Test (DCCS). DCCS is a measure of cognitive flexibility. Two target pictures are presented that vary along two dimensions (e.g., shape and color). Participants are asked to match a series of bivalent test pictures (e.g., yellow balls and blue trucks) to the target pictures, first according to one dimension (e.g., color) and then, after a number of trials, according to the other dimension (e.g., shape). "Switch" trials are also employed, in which the participant must change the dimension being matched. For

example, after 4 straight trials matching on shape, the participant may be asked to match on color on the next trial and then go back to shape, thus requiring the cognitive flexibility to quickly choose the correct stimulus. Scoring is based on a combination of accuracy and reaction time.

**Processing Speed (NIH Toolbox).** Processing Speed is either the amount of time it takes to process a set amount of information, or, the amount of information that can be processed within a certain unit of time. It is a measure that reflects mental efficiency, and will be measured with the [NIH Toolbox Pattern Comparison Processing Speed Test](#). This test measures speed of processing by asking participants to discern whether two side-by-side pictures are the same or not. Participants' raw score is the number of items correct in a 90-second period. The items are designed to be simple to most purely measure processing speed.

**2. Motor.** Motor function will be assessed using the NIH Toolbox tests to evaluate 1) dexterity and 2) strength.

**Dexterity (NIH Toolbox):** Dexterity is the coordination of small muscle movements, which occur in body parts. Dexterity is measured by the [NIH Toolbox 9-Hole Pegboard Dexterity Test](#). This simple test records the time required for the participant to accurately place and remove 9 plastic pegs into a plastic pegboard. The protocol includes 1 practice and 1 timed trial with each hand. Raw scores are recorded as time in seconds that it takes the participant to complete the task with each hand (a separate score for each).

**Strength (NIH Toolbox):** Strength refers to a muscle's ability to generate force against physical objects. Measuring hand grip shows how strong ones hand grip is, which in turn provides a good approximation of overall muscle strength. Strength is measured by the [NIH Toolbox Grip Strength Test](#). Participants are seated in a chair with their feet touching the ground. With the elbow bent to 90 degrees and the arm against the trunk, wrist at neutral, participants squeeze the Jamar Plus Digital dynamometer as hard as they can for a count of three. The dynamometer provides a digital reading of force in pounds. A practice trial at less than full force and 1 test trial are completed with each hand.

